6.1.2 Ancillary treatments

Any additional therapy aimed to treat anemia and cytopenias during this trial (i.e. recombinant growth factors, steroids or immunosuppressive therapy for the improvement of hematological parameters) is not allowed, except study medication. Steroid treatment for chronic medical conditions is allowed if stable or improving over at least 2 months prior to screening. No RBC transfusions are allowed after randomization. Patients who are RBC transfusion dependent must not be enrolled in the study. Patients must be withdrawn from the study anytime when transfusion as rescue therapy is needed.

No other iron chelation therapy is allowed while patients are receiving study treatment in this trial.

6.1.3 Guidelines for continuation of treatment

For patients who are unable to tolerate the protocol-specified dosing schedule, dose reductions are permitted in order to keep the patient on study drug. These changes must be recorded on the dosage administration record eCRF.

The majority of dose reductions are covered in Section 6.3.1. For all cases where a dose adjustment is considered necessary but is not covered in the following sections, the investigator will send a written request to Novartis. The request must justify the dose change and provide all the supportive clinical and laboratory information for complete evaluation by Novartis. Any dose adjustment for reasons not included in this section needs to be authorized by Novartis. A written reply will be promptly sent back to the investigator by Novartis.

6.1.4 Treatment duration

The whole treatment period will last 24 week. The primary objective (erythroid response according to IWG criteria: Hb increase ≥ 1.5 g/dL) will be assessed by 12 weeks of treatment. At any time, if Hb ≥ 12 , EPO will be stopped until the end of study. These patients will be considered as responders.

By 24 weeks, patients initially assigned to the combination therapy who showed Hb increase ≥ 1 g/dL by week 12 will be assessed for full hematological response according IWG criteria (Erythroid response: Hb increase from baseline ≥ 1.5 g/dL; Neutrophil response: increase from baseline of $\geq 100\%$ and $> 0.5 \times 10^9/L$; Platelet response: increase from baseline of $\geq 30 \times 10^9/L$).

If after 12 weeks of treatment with EPO alone, Hb increase is < 1 g/dL and total Hb is < 12 g/dL, the patient will switch to the combination therapy with EPO and DFX for the remaining 12 weeks and will be assessed for erythroid response by 24 weeks. If after 12 weeks of treatment with EPO in combination with DFX, Hb increase is < 1 g/dL and total Hb is < 12 g/dL, the patient will be discontinued from the study.

Subjects need to be discontinued from the study if at least one of the following occurs:

- $\geq 50\%$ decrement from maximum response levels in granulocytes or platelets
- Reduction of Hb level ≥ 1.5 g/dL compared to best response
- Patient requiring blood transfusion at any time

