2.3 Rationale for dose and regimen selection

EPO treatment is used in MDS patients early after the diagnosis to induce erythroid response and alleviate the symptoms of anemia. At this stage, iron overload is not expected to be high. In addition, the mechanism by which DFX might be efficacious in this setting is related to the depletion of toxic free iron and possibly to the inhibition of NF- κ B in the malignant cells. High doses of DFX are not required to achieve these objectives. Therefore, the dose of DFX DT is established at 10 mg/kg/day and the dose of DFX FCT is established at 7 mg/kg/day.

The current practice for the use of EPO is so variable and differs among countries and even among physicians. Therefore the dose of EPO in this study is chosen based on the guidelines (ASH-ASCO) published by David McCulloch in 2010. According to that, the starting dose in this study is 40,000 units/week. If increase in Hb is < 1 g/dL and total Hb is < 12 g/dL after 4 weeks, the dose should be increased to 60,000 units/week. If increase in Hb is ≥ 1 g/dL and total Hb is < 12 g/dL, patients should continue the current EPO dose. If Hb increase is ≥ 1 g/dL and total Hb is ≥ 12 g/dL, the patients should hold EPO treatment.

Dose change after 12 weeks of study treatment will also be performed according to the EPO guidelines (Appendix 3). If Hb increase is ≥ 1 g/dL and total Hb is < 12 g/dL, patients should continue the current EPO dose. If Hb increase is ≥ 1 g/dL and total Hb is ≥ 12 g/dL, the patients should hold EPO dose (Table 4-1). According to the EPO guidelines, if after 12 weeks of treatment with EPO, Hb increase is < 1 g/dL and total Hb < 12 g/dL, the patient should discontinue EPO as the patient is not responding. In this study, those patients who do not respond to 12-week-EPO treatment will not be discontinued, but they will be switched to the combination for another period of 12 weeks.

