As the EPO guidelines only provide guidance for EPO use (EPO dosing, dose adjustments and dose discontinuation) and do not specify any criteria for the evaluation of erythroid response in MDS patients, in this study, the primary objective erythroid response will be assessed according to IWG criteria (Hb increase ≥ 1.5 g/dL) at 12 weeks of treatment. At any time, if Hb ≥ 12 g/dL, EPO will be stopped until the end of study. Patients treated with the combination therapy will stop EPO if Hb ≥ 12 g/dL and continue on DFX.

At 24 weeks, patients initially assigned to the combination therapy who showed Hb increase ≥ 1 g/dL at week 12 will be assessed for full hematological response according to IWG criteria (Erythroid response: Hb increase from baseline ≥ 1.5 g/dL; Neutrophil response: increase from baseline of $\geq 100\%$ and $> 0.5 \times 10^9/L$; Platelet response: increase from baseline of $\geq 30 \times 10^9/L$).

Patients initially treated with EPO alone and switched to the combination therapy with EPO and DFX after 12 weeks will be assessed for erythroid response at study end after 24 weeks of study treatment.

Figure 4-1 Study Design

Pre-treatment phase (Screening)

At Screening Visit (Visit 1) the investigator or his/her designee will assign a unique number to patients being considered for the study.

Prior to performing any study-related procedures or assessments, the patient must provide written consent to participation in this study. A screening period (up to 28 days) will be used to assess patient eligibility. Two Screening Visits will be required because key safety parameters need to be performed twice before the first dose administration ([Table 7-1](#)).

This study will use an Interactive Web Response (IWR) technology for randomization. Once the patient provides a signed informed consent form and eligibility is confirmed (all inclusion/exclusion criteria have been verified) the investigator and/or his designee can register the patient using the IWR.

Treatment phase

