	Hb increased < 1 g/dL from baseline and Hb < 12 g/dL	Increase EPO to 60,000 units/week *
	Hb increase is ≥ 1 g/dL and Hb < 12 g/dL	Continue EPO 40,000 units/week *
	Hb increase is ≥ 1 g/dL and Hb ≥ 12 g/dL	Hold EPO treatment *
Week 12	Hemoglobin status	Action
	Hb increased < 1 g/dL from baseline and Hb < 12 g/dL	If patient is in the combination arm: Discontinue from the study or If patient is in the EPO monotherapy arm: Switch to the combination EPO + DFX
	Hb increase is ≥ 1 g/dL and Hb < 12 g/dL	Continue current EPO dose *
	Hb increase is ≥ 1 g/dL and Hb ≥ 12 g/dL	Hold EPO treatment *

* Patients in combination arm will continue DFX DT 10 mg/kg/day or DFX FCT 7 mg/kg/day treatment

[figure not shown]
The primary objective (erythroid response according to IWG criteria: Hb increase ≥ 1.5 g/dL) will be assessed at 12 weeks of treatment. At any time, if Hb ≥ 12 g/dL, EPO will be stopped until the end of study.

At 24 weeks, patients initially assigned to the combination therapy who showed Hb increase ≥ 1 g/dL at week 12 will be assessed for full hematological response according IWG criteria (Erythroid response: Hb increase from baseline ≥ 1.5 g/dL; Neutrophil response: increase from baseline of ≥ 100% and > 0.5 x 10⁹/L; Platelet response: increase from baseline of ≥ 30 x 10⁹/L). Patients initially treated with EPO alone and switched to the combination therapy with EPO and DFX after 12 weeks will be assessed for erythroid response according to IWG criteria after 24 weeks.

No RBC transfusions are allowed after randomization, as transfusions would affect the endpoints of the trial. Patients who are RBC transfusion dependent must not be enrolled in the study. RBC transfusion dependence is defined as more than 2 units RBC /4 weeks at any time during the last 12 week period prior to study entry (Gale 2011). Patients must be withdrawn from the study anytime when transfusion as rescue therapy is needed.

Safety assessments are routinely performed including collection of AEs, SAEs, vital signs, physical examination, ECG, hematological and biochemistry assessments.

Patients will continue therapy until disease progression or intolerable toxicity, patient decision or death, after 12 weeks of combination treatment without response or after 24 weeks treatment duration at which point an End of Treatment (EOT) Visit will be performed and the End of Treatment CRF page will be completed.

30 day follow-up

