S21	Epo dose reduced below assigned dose as per protocol for more than 1 week in period week 1-12	Report as PD, include in FAS and Safety Set.
S22	Epo dose reduced below assigned dose as per protocol for more than 1 week in period week 13-24	Report as PD, include in FAS and Safety Set.
S23	Epo dose increased above assigned dose as per protocol for more than 1 week in period week 1-12	Report as PD, include in FAS and Safety Set.
S24	Epo dose increased above assigned dose as per protocol for more than 1 week in period week 13-24	Report as PD, include in FAS and Safety Set
S03	Epo dose maintained at 40.000 units/week and not increased to 60.000 units/week after 4 weeks as per protocol for more than 1 week but Hb increase < 1 g/dL and total Hb < 12 g/dL	Report as PD, include in FAS and Safety Set.
S05	Epo dose increased to 60.000 units/week and not maintained at 40.000 units/week after 4 weeks as per protocol for more than 1 week but Hb increase ≥ 1 g/dL and total Hb < 12 g/dL	Report as PD, include in FAS and Safety Set.
S06	Patient randomized to monotherapy not switched to combination therapy as per protocol or switch delayed for more than 1 week after 12 weeks of treatment but Hb increase < 1 g/dL and total Hb < 12 g/dL	Report as PD, include in FAS and Safety Set.
D12	Patient randomized to combination therapy not discontinued after 12 weeks of treatment as per protocol or discontinuation delayed for more than 1 week but Hb increase < 1 g/dL and total Hb < 12 g/dL	Report as PD, include in FAS and Safety Set.
S10	Patient randomized to combination therapy stopped DFX treatment for more than 1 week in period week 1-12 not as per protocol	Report as PD, include in FAS and Safety Set.
S25	Patient assigned to combination therapy stopped DFX treatment for more than 1 week in period week 13-24 not as per protocol	Reported as PD, include in FAS and Safety Set.
M01	Forbidden concomitant medication as per	Report as PD,

	protocol	include in FAS and Safety Set.
M02	Patient received iron chelation therapy other than the study treatment	Report as PD, include in FAS and Safety Set.
D01	Transfusion during the study but not withdrawn	Report as PD, include in FAS and Safety Set.
D02	Pregnancy during the study, but not withdrawn	Report as PD, include in FAS and Safety Set.
S11	Patient randomized but received wrong study drug	Report as PD, include in FAS and Safety Set.

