D03	≥50% decrement from maximum response levels in granulocytes or platelets but patient not withdrawn	Report as PD, include in FAS and Safety Set.
D04	Reduction of Hb level ≥1.5g/dL compared to best response but patient not withdrawn	Report as PD, include in FAS and Safety Set.
D05	Consent withdrawn but patient not withdrawn	Report as PD, Exclude from all analyses.
S12	Deferasirox dose was not reduced despite serum creatinine increase of ≥33% above baseline and above ULN at 2 consecutive occasions	Report as PD, include in FAS and Safety Set.
S13	Deferasirox treatment was not interrupted despite severe case of skin rash	Reported as PD, include in FAS and Safety Set.
S14	Deferasirox treatment was not interrupted despite persistent and progressive increase in serum transaminase levels that cannot attributed to other causes	Report as PD, include in FAS and Safety Set.
S15	Deferasirox treatment was not interrupted despite unexplained cytopenia	Report as PD, include in FAS and Safety Set.
S16	Deferasirox dose not recalculated despite > 10% change in body weight	Report as PD, include in FAS and Safety Set.
S17	Deferasirox treatment was not interrupted despite severe hypersensitivity reactions	Reported as PD, include in FAS and Safety Set.
S18	Deferasirox treatment was not permanently discontinued despite suspected Stevens Johnson syndrome	Report as PD, include in FAS and Safety Set.
G01	Use of local laboratory instead of central laboratory	Report as PD, include in FAS and Safety Set.
G03	Patient was randomized with missing central lab results and/or based on local lab results	Reported as PD, include in FAS and Safety Set.

The RAP module 8 will include variables that will flag the missing values at baseline for the laboratory parameters or flag corresponding to certain assessments which leads to the exclusion of the patient from any analyses.

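### The treatment sections tell sites both to switch and to discontinue an EPO-arm patient whose haemoglobin has fallen back by week 12, and they state no order between the two rules

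*Protocol*

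**What the plan says.** **Switch.** For a week-12 Hb rise below 1 g/dL with Hb below 12 g/dL, Table 4-1 says: "If patient is in the EPO monotherapy arm: Switch to the combination EPO + DFX". Section 6.1.4 repeats that "the patient will switch to the combination therapy with EPO and DFX for the remaining 12 weeks". Section 2.3, contrasting the trial with the EPO guideline, says these patients "will not be discontinued, but they will be switched to the combination for another period of 12 weeks".

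**Discontinue.** A few lines after its switch rule, section 6.1.4 says "Subjects need to be discontinued from the study if at least one of the following occurs". One item on the list is "Reduction of Hb level ≥ 1.5 g/dL compared to best response". The list is not limited by arm or by time, and *best response* is not defined.

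**Stop EPO.** Section 4.1 says: "At any time, if Hb ≥ 12 g/dL, EPO will be stopped until the end of study". Section 6.1.4 repeats this and counts such patients as responders. The week-12 switch row of Table 4-1 makes no exception for them.

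**Analysis and deviations.** Protocol 10.5.2 and SAP 2.9.2.2 require week-12 EPO-arm non-responders to switch provided they stay in the study. SAP Table 4-7 makes two events reportable: S06, "Patient randomized to monotherapy not switched to combination therapy as per protocol or switch delayed for more than 1 week" (with rise below 1 and Hb below 12), and D04, "Reduction of Hb level ≥1.5g/dL compared to best response but patient not withdrawn".

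**The concern.** Both actions are mandatory and they exclude each other: a patient cannot be withdrawn and also be treated with EPO+DFX for 12 more weeks. The clash arises only in the control arm, because in the combination arm a week-12 rise below 1 g/dL (with Hb below 12) already ends in discontinuation.

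Sites that resolve it differently will differ in who receives DFX, who leaves the study, and who makes up the switched cohort. That cohort supplies the response rate in 10.5.2, the time to response in 10.5.5 and part of the duration analysis in 10.5.8. It is described as non-responders to EPO. Under 10.4.1, however, a rise of 1.5 g/dL or more at any time in the first 12 weeks makes a patient a primary-endpoint responder. A patient who rose that far and fell back could be counted as a responder in the primary analysis and then enter the non-responder cohort at one site, but be withdrawn at another.

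**Working it through.** The plan gives no figure to reproduce, so the check is whether the rules overlap and under what conditions.

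**Notation.** B = baseline Hb, P = highest earlier on-study Hb, W = week-12 Hb (g/dL).

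- Switch (Table 4-1, 6.1.4): W − B < 1 and W < 12.
- Discontinue (6.1.4): P − W ≥ 1.5.
- Narrow reading of *best response* (a prior response is needed): also P − B ≥ 1.5.

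The condition W < 12 adds nothing. Inclusion criterion 5 with its 5% tolerance keeps B at or below 10.5, so a rise below 1 keeps W below 11.5.

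**Worked courses**

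| B | P | W | W − B | P − W | P − B | Result |
|---|---|---|---|---|---|---|
| 9.0 | 10.7 | 9.1 | 0.1 | 1.6 | 1.7 | both rules, either reading; primary responder |
| 9.0 | 11.0 | 9.4 | 0.4 | 1.6 | 2.0 | both rules, either reading; primary responder |
| 9.0 | 9.8 | 8.3 | −0.7 | 1.5 | 0.8 | both rules only if *best response* means best Hb |
| 10.2 | 12.0 (week 4) | 11.1 | 0.9 | 0.9 | 1.8 | switch row met, no Hb-fall rule, EPO already stopped |
| 9.7 | 12.0 (week 4) | 10.6 | 0.9 | 1.4 | 2.3 | same, without using the eligibility tolerance |

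The last two rows show that the EPO-stop conflict stands apart from the Hb-fall rule. The switch row calls for EPO+DFX, while 4.1 and 6.1.4 allow no more EPO. With a peak of at least 12 and a fall below 1.5, W exceeds 10.5. A rise below 1 then needs B above 9.5, which the entry range allows.

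**Timing.** If the fall was already visible at an earlier visit, 6.1.4 should have removed the patient before week 12. The two instructions collide at week 12 only when the fall is first seen there.

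**Frequency, under assumptions.** The documents give no within-patient Hb variability. The simulation used 400,000 patients per scenario, independent normal errors on the baseline reading and on readings at weeks 2, 4, 6, 8 and 12, and a flat true Hb. Percentages are of patients due to switch; in the last row, of those not already due to leave under the Hb-fall rule.

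| Reading of *best response* | SD 0.4 | SD 0.6 | SD 0.8 |
|---|---|---|---|
| Any best Hb, met at week 12 | 1.5% | 13% | 29% |
| Prior rise ≥ 1.5 needed | 0.1–0.2% | 3.4% | 11% |
| Prior rise ≥ 1.5 needed, fall first seen at week 12 | 0.1% | 1.9% | 5.5% |

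With a true decline of 1 g/dL over 12 weeks, the first row becomes 18 / 36 / 49% and the last 0.1 / 1.0 / 3.0%. The SD applies to each reading, so the difference between two readings has an SD 1.41 times larger. Every simulated patient has a week-6 reading, although Visit 8 takes place only after an EPO increase.

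**Weight in the cohort.** At 1:1, 60 patients give about 30 on EPO alone. If 15 switched (an assumption), two affected patients would be 2/15 = 13% of the switched cohort.

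**The case against.** The best defence is that the documents allow a coherent reading. Protocol 10.5.2 and SAP 2.9.2.2 make the switch conditional on staying in the study, and a patient discontinued under 6.1.4 is not staying. Section 4.1 continues therapy only until progression, and Appendix 2 lists an Hb reduction of 1.5 g/dL or more as progression or relapse after improvement. The statement in 2.3 that patients are not discontinued contrasts the trial with the guideline's stop for non-response; it was not written about the Hb-fall rule. Section 7.1.3.1 omits the Hb-fall rule but permits withdrawal for abnormal laboratory values or unsatisfactory effect, so it does not contradict it.

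Much of this stands, and it rules out some stronger conclusions that a reader might draw:

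- *That either action is a reportable deviation.* Switching and keeping the patient is D04 without qualification. Withdrawing is S06 only on a literal reading, because S06 refers to not switching as per protocol and a patient withdrawn under 6.1.4 can be said to have been handled that way.
- *That nothing in the documents bears on the order.* The analysis sections do. But the condition appears only there and not in the treatment instructions that sites follow.
- *That the overlap is common.* The larger percentages need the broad reading of *best response*. Appendix 2 and the relapse definition in Table 3-1, which is measured from Hb at response, favour the narrow one. A scenario with a 2 g/dL rise lost by week 12 gives 85 to 87%, but it assumes the conflict.
- *That a patient with EPO stopped at Hb 12.1 who falls from there to 10.2 (baseline 9.5) faces three live instructions.* If discontinuation is followed, the other two lapse. The courses 10.2, 12.0, 11.1 and 9.7, 12.0, 10.6 are the cleaner examples.

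The cohort analyses are also descriptive and secondary, in a pilot, and the week-12 primary endpoint is not affected.

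**Conclusion.** The conflict is real but narrower than it first looks. The treatment sections give one EPO-arm patient two mandatory, incompatible actions and state no order. The overlap survives the narrow reading of *best response*. A second, separate gap concerns patients whose EPO was stopped at Hb 12 or more and who later meet the switch row.

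The consequence is an ill-defined switched cohort in 10.5.2, 10.5.5 and 10.5.8, which may include patients already counted as primary responders, and a deviation listing that depends on how S06 is read. How often this happens cannot be known from the documents. On flat Hb with assumed SDs of 0.4 to 0.8 g/dL, the range is about 0.1 to 5.5% of patients due to switch (prior response required, fall first seen at week 12) to 1.5 to 29% (any best Hb). The case for correcting the text rests on the contradiction itself and does not depend on these percentages.

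**What to change.** 1. Reconcile protocol 2.3, 4.1 with Table 4-1, 6.1.4, 7.1.3.1 and 10.5.2, and SAP 2.9.2.2, under one stated order of precedence. It should cover an EPO-arm patient who meets both the switch rule and the Hb-fall rule, and one whose EPO was already stopped for Hb of 12 or more. Which rule takes precedence is a clinical decision for the sponsor; this review does not propose one.
2. State whether *best response* means the highest on-study Hb or applies only after a response.
3. Align SAP codes S06 and D04 so that a patient handled under the stated order is not listed as a deviation.
4. Beside the switch-phase response rate, report how many patients met both rules and how many in the switched cohort were already primary-endpoint responders.

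The cost is protocol and SAP wording, two deviation codes and two counts from Hb data already collected. No extra patients or assessments are needed.

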6.2 Dose escalation guidelines

Not applicable.

6.3 Dose modifications

6.3.1 Dose modification and dose delay

For patients who do not tolerate the protocol-specified dosing schedule, dose reductions are permitted in order to allow the patient to continue the study treatment. The following guidelines need to be applied:

During the study, the dose of DFX DT must not be escalated above 10 mg/kg/day or the dose of DFX FCT above 7 mg/kg/day. The standard dose of DFX DT 10 mg/kg/day or DFX FCT 7 mg/kg/day may be reduced as part of the management of side effects. No dose changes based on efficacy parameters are permitted. Dose adjustments in increments of 5 or 10 mg/kg for DFX DT and of 3.5 or 7 mg/kg for DFX FCT may be made as part of adverse events management.

These changes must be recorded on the Dosage Administration Record CRF.

The majority of dose adjustments are covered in the [Section 6.3.1](#) below. For cases where an exceptional dose adjustment (i.e., an adjustment not covered in the following sections) is considered necessary, the investigator will send a written request to Novartis. The request must justify the dose change and provide all the supportive clinical and laboratory information for complete evaluation by Novartis. Any exceptional dose adjustment needs to be authorized by Novartis. A written reply will be sent back to the investigator by Novartis within 5 working days.

